We will partner with BroadReach Healthcare, a PEPFAR partner in South Africa, to pilot test an innovative index partner HIVSS strategy in one urban and one rural public health clinic in the Nkangala district of Mpumalanga Province to evaluate **acceptability, barriers, and preliminary efficacy** of secondary HIVSS distribution in a randomized control trial enrolling women newly diagnosed with HIV or on ART. In the intervention arm, women will receive counselling on how to use HIVSS, how to encourage their male partner to screen, and 2 HIVSSs with HIVSS instructions and invitation to return for confirmatory testing. In the standard of care arm, index women will receive counselling on the importance of disclosure to their family and partner(s) and referral for HIV testing (per SA national guidelines). We will evaluate the following aims:

1. Conduct a mixed-methods survey with N=100 HIV+ women to assess perceived **acceptability and barriers** (including perceived safety, IPV) to secondary HIVSS distribution by women to male partners.
2. Test the **feasibility** and **preliminary efficacy** of secondary HIVSS distribution through a 1:1 randomized control trial in n=100 HIV+ women to assess, comparing standard of care to intervention arm:
 - a. % of index women who self-report that they gave the HIVSS or standard of care referral for testing to their male partner
 - b. % of male partners who either screened or tested for HIV assessed at 3 months after randomization (*primary outcome*)
 - i. Measured via options of: index or partner self-report, SMS/WhatsApp of a picture of the used HIVSS sent by partner or index, return of a used self-test to the facility by either the index or partner, and/or partner coming into facility for with an invitation for confirmatory testing or SOC counseling referral
 - c. % of male partners with a positive HIV screening/test result
 - d. % of newly diagnosed male partners who initiate ART within 3 months of diagnosis
 - e. % of those on ART with viral suppression after 6 months on ART (index and partners)
3. In the intervention arm, we will assess acceptability and barriers (including safety/IPV) related to HIVSS distribution or use via surveys with all intervention participants who return for the study endline survey and a convenience samples of n=20 male partners (n=10 men who used HIVSS and n=10 men who did not use HIVSS)

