We will publish these results to inform PEPFAR index and HIVSS implementation in South Africa. This study will inform a larger trial to apply for a large research grant to the US National Institute of Health (NIH) in late 2021.

3. Study design

Randomized control trial of n=100 WLHIV (50 in each arm) in two facilities in the Nkangala district. We selected high-density facilities, Kwamhlanga CHC and Sr Mashiteng Clinic facility from a rural and urban area, respectively, to ensure that the results are generalizable. These facilities use oral HIV test kits, which has been shown to be more acceptable in terms of ease of use (20, 21). WLHIV will be recruited in antenatal care or in HIV care services. Inclusion criteria are listed below.

Inclusion Criteria:

1. Adult female 18+ years old
2. confirmed HIV-positive or on ART
3. confirmed to currently have a male partner and are sexually active
4. male partner is of HIV- or unknown status
5. confirmed to have a cell phone that can read and respond to SMS/WhatsApp messages
6. confirmed to be able to consent to study participation (no language constraints or psychological issues that would make it difficult to consent to participate in the study)

Exclusion criteria: Failure to meet all of inclusion criteria

Procedures for the informed consent process are outlined below. Throughout, trained BroadReach staff will ensure that women are aware of their right to refuse and/or withdraw from the study at any time. In addition, study staff will emphasize that all study activities are entirely separate from routine HIV care services received and that refusal or withdrawal from the study will have no impact on their ability to access any services provided at any public-sector health facility.

Study procedures

The study will be integrated into Kwamhlanga CHC (rural facility) and Sr Mashiteng Clinic facility (urban facility) in Nkangala district. WLHIV will be recruited directly from the clinic HCT, antenatal care, or ART services. All trained staff are already working in the facility part of the ongoing current APACE (Accelerating Programme Achievements to Control the Epidemic) programme under USAID. The trained study recruiter will recruit eligible directly from women in the study, and if interested and eligible after the screening process, the women will go to a private room for the study consent and interview.

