Baseline survey: After consent, a trained interviewer/counselor will administer a brief 10-15 minute survey to n=100 WLHIV about socio-demographics (age, education, relationship status), knowledge of partner's prior HIV testing and status, willingness to distribute HIVSS to their partner(s), facilitators/barriers to HIVSS (17). A trained study staff will ask the survey questions in the local dialect using RedCap. Participants will receive an option to participate in the interview on the phone instead of returning to the health facility.

Randomization: Following the baseline survey, women will be randomized to receive a HIVSS or referral in a 1:1 ratio to the intervention or standard of care arm. Randomization will be performed using a random number table by participant ID, who will be provided with sealed randomization envelopes. The participants will open the envelopes sequentially.

Male partner contact: For women allocated to the intervention arm, the participant will be given a HIVSS to take home to their partner(s). The counsellors will give the participant two options for contacting their partners:

- The participant will contact their partner (via a telephone call or SMS) while in the counselling session to confirm the partner's participation and obtain permission to provide his contact details.
- The participant will ask the partner to contact the counsellor to confirm participation and provide his contact details. If the participant confirms that her partner consented to participate in the study, the counsellor will call him to request his consent over the phone and confirm that he is her partner (using his name and date of birth). The interviewer will read the consent form on the phone and send him a copy via SMS/WhatsApp or email.

Standard of care arm: In the standard of care arm, women will receive standard of care partner referrals for HIV testing, including counselling about disclosure and referral for her partner(s) to return to the facility for testing. They will complete an endline survey after ~3 months (or when they return for their next clinical visit, ART start, or drug pick up visit) to evaluate the uptake of partner testing, results, and safety, including IPV.

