Randomize n=100 WLHIV to intervention vs standard of care			X	X			
Deliver HIVSS and instructions to n=50 and referral counseling to n=50			X	X			
Follow up participants at ~3 months (to coincide with next clinical visit) to conduct endline survey and evaluate HIV testing uptake, results					X	X	X

(positivity) and linkage (telephonically and using health records)						
Study endline survey for n=20 partners in the intervention arm (telephonically)				X	X	X
Analysis and dissemination					X	X

Evaluation: We will evaluate the following outcomes in the study including:

1. % of index women who self-report that they gave the HIVSS or SOC counseling referral to their male partner
2. % of male partners who either screened or tested for HIV assessed at 3 months after randomization (primary outcome)
 - i. Outcome measured via: index or partner self-report, SMS/WhatsApp of a picture of the used HIVSS sent by partner or index, return of a used self-test to the facility by either the index or partner, and/or partner coming into facility for with an invitation for confirmatory testing or SOC counseling referral
3. % of male partners with a positive HIV screening/test result (case finding)
4. % of newly diagnosed male partners who initiate ART within 3 months of diagnosis
5. % of those on ART with viral suppression after 6 months on ART (index and partners)

4. Ethical considerations

The study protocol, informed consent form, all data collection tools, and other requested documents will be reviewed and approved by the University of Cape Town Faculty of Health Sciences Human Research Ethics Committee (UCT-HREC).

Informed consent

The study informed consent for the study and questionnaire are modelled after that used in previous studies and will be delivered in participants' home language by trained interviewers. The informed consent form (ICF) will be translated into isiZulu and back-translated into English to confirm accuracy. This study ICF details the purpose of the study, study procedures, and the risks and benefits to women that participants may encounter at the second study visit. We will ask women if they want to consent to give her partners' contact information (phone number), but this will not be required to join the study.

Here, study staff will emphasize to participants that:

- Participation is entirely voluntary, and their choice regarding participation will in no way influence the quality of routine medical care for mothers

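### The primary comparison has no covariate adjustment or stratification, although the woman's report of her partner's testing and status is already collected before randomisation

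*Combined protocol and SAP*

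**What the plan says.** - **Design.** Study design gives a "Randomized control trial of n=100 WLHIV (50 in each arm) in two facilities in the Nkangala district".
- **Outcome.** Study Objectives (aim 2b) and Evaluation (outcome 2) define the primary outcome as the percentage "of male partners who either screened or tested for HIV assessed at 3 months after randomization (primary outcome". Aim 2 adds only that it is for "comparing standard of care to intervention arm". No test, model, effect measure, interval or covariate list is given.
- **Randomisation.** Under Study procedures, women are allocated "in a 1:1 ratio to the intervention or standard of care arm". "Randomization will be performed using a random number table by participant ID", with sealed envelopes. No stratification by partner history or facility is stated.
- **Baseline data.** The Baseline survey paragraph has all 100 women asked about their "knowledge of partner's prior HIV testing and status". The Randomization paragraph puts allocation after that survey.
- **Eligibility.** Inclusion criterion 4 limits the partner's status to negative or unknown.

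**The concern.** With 50 women per arm and no stratification, a baseline factor that predicts partner testing can differ noticeably between arms by chance. The realised difference then carries that imbalance, and the document says this pilot is to inform a larger trial. The woman's report about her partner's testing and status is a natural candidate for such a factor. It is measured before allocation, so it can be adjusted for without risk of being affected by treatment. At stake is some precision that needs no extra recruitment, together with the chance to fix the covariate before anyone has seen results by arm.

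**Working it through.** The document gives no power, effect size or expected testing rates, so there is no stated figure to reproduce.

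**Inputs from the document:** 50 women per arm; 1:1 allocation; binary outcome at 3 months.

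**Assumptions:** control versus intervention testing of 30% v 60% or 50% v 75%; a binary baseline factor with prevalence q of 30% or 50%; a within-arm difference in testing between its two levels (delta) of 0 to 40 points; no dropout.

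**Step 1. Chance imbalance.** With the factor present in K = 100q women and 100 women split 50/50, the number in one arm is hypergeometric (100, K, 50).

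| q | SD of difference | P(≥10 points) | P(≥15 points) | P(≥20 points) |
|---|---|---|---|---|
| 50% | 10.1 points | 32% | 16% | 7% |
| 30% | 9.2 points | 27% | 13% | 5% |

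The unadjusted difference shifts by imbalance × delta. A 20-point imbalance gives 0.20 × 0.20 = 4 points, or 0.20 × 0.40 = 8 points.

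**Step 2. Precision without adjustment.** Variance = [p0(1 − p0) + p1(1 − p1)]/50. For 30% v 60%: (0.21 + 0.24)/50 = 0.0090, so the 95% half-width is 1.96 × 0.0949 = 18.6 points.

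**Step 3. Precision with adjustment.** Each arm's outcome variance falls by q(1 − q) × delta². At q = 50%:
- delta = 20 points: reduction per arm 0.25 × 0.04 = 0.01. Variance (0.20 + 0.23)/50 = 0.0086, down 0.02/0.45 = 4.4%.
- delta = 40 points: reduction per arm 0.25 × 0.16 = 0.04. Variance (0.17 + 0.20)/50 = 0.0074, down 0.08/0.45 = 17.8%.

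| Rates (q = 50%) | Half-width, unadjusted | delta = 20 points | delta = 40 points |
|---|---|---|---|
| 30% v 60% | 18.6 | 18.2 (variance −4.4%) | 16.9 (variance −17.8%) |
| 50% v 75% | 18.3 | 17.9 (variance −4.6%) | 16.6 (variance −18.3%) |

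For 30% v 60%, the effective size is 50/(1 − 0.044) = 52 per arm or 50/(1 − 0.178) = 61 per arm. At q = 30% the reductions are 3.7% and 14.9%.

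**Step 4. Cost of estimating the adjustment.** Step 3 ignores the price of estimating the covariate's coefficient. In 40,000 simulated trials per scenario (30% v 60%, q = 50%, linear adjustment), the ratio of adjusted to unadjusted variance was 1.012 for delta = 0, 0.964 for 20 points and 0.832 for 40 points. The mean estimate was 30 points with and without adjustment. With two covariates that predict nothing, the crude-to-adjusted variance ratio was 0.98, a loss of about 2%.

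**Step 5. Break-even.** At delta = 10 points, Step 3 gives 2 × 0.25 × 0.01/0.45 = 1.1%, about equal to the 1.2% cost in Step 4. Under these assumptions the factor has to be worth more than roughly 10 points before adjustment gains anything.

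**The case against.** Four objections carry weight.

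- **The plan does not choose a crude comparison.** A reader might infer from an outcome stated as a percentage by arm that the analysis is to be unadjusted. The text does not say so; it names no method at all. The absence of a primary analysis method is the wider gap, and this point is one detail inside it. This stands.
- **The result is not biased.** A reader might infer that chance imbalance biases the comparison. Over repeated randomisations it does not, and the unadjusted interval already allows for it. Even an 8-point shift is under half of the 18.6-point half-width, and it needs both a 40-point factor and an imbalance seen in about 7% of trials. This stands.
- **The survey item is not a baseline measurement of the outcome.** It is what the woman knows or believes. An unknown status can cover a man never tested and a man who tested without telling her. That limits its likely strength as a predictor, but not its validity as a covariate measured before randomisation.
- **Newly diagnosed versus on ART is not a ready second covariate.** Study Objectives describes "enrolling women newly diagnosed with HIV or on ART", but inclusion criterion 2 asks only for confirmed HIV infection or ART use. A woman diagnosed earlier and not on ART fits neither group, and one who has just started may fit both. The listed survey content includes no diagnosis date or time on ART. A reader might also suppose that women on ART have had partner-testing advice before. The document does not say so, and its background states that index partner testing has not been scaled up in the province.

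A plain risk difference with an interval would therefore be defensible in a pilot of preliminary efficacy. What remains is that a usable item is already collected, adjustment costs little at worst, and it helps moderately if the item is strongly predictive.

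**Conclusion.** The point holds as a modest, inexpensive improvement, not as an error that invalidates the comparison. Neither the stated randomisation nor the stated outcome comparison uses the reported partner testing/status. For 30% v 60% and 50% prevalence, the formula puts the gain at about 4% of variance for a 20-point factor and 18% for a 40-point factor, at most about 2 points of half-width. If the item is weakly predictive or not predictive, about 1-2% is lost. All of these sizes rest on assumed testing rates, prevalence and predictive strength, none of which the document gives. A reader might infer that precision is certain to improve; it improves only if the item predicts well enough.

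**What to change.** Add a paragraph to the Evaluation section that:

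1. makes the primary estimate the risk difference with 95% CI, standardised for reported partner testing/status by g-computation, or by linear regression with centred covariates and robust errors;
2. fixes before data lock how the covariate is coded, including whether 'don't know' is its own level or is merged with 'unknown';
3. reports the crude percentages and the unadjusted difference alongside;
4. keeps the covariates few. Facility, which Study design already identifies as rural or urban, may be added. Newly diagnosed versus on ART should enter only if it is defined and recorded at baseline.

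The cost is one paragraph of text and about 1-2% of precision if the covariate turns out to predict weakly or not at all. Reported partner testing/status and facility need no new data and no extra women.

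### In the intervention arm, a kit used by the index woman herself can count as her partner's test, because outcome 2(i) accepts a used kit or photo from her without asking who used it

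*Combined protocol and SAP*

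**What the plan says.** Outcome 2(i) appears twice with the same content: under Study Objectives, aim 2(b)(i), and under Evaluation. It lists the evidence that the partner screened or tested:

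- "index or partner self-report"
- a kit photo messaged to staff by either member of the couple
- "return of a used self-test to the facility by either the index or partner"
- the partner's own visit to the facility with an invitation or referral

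The routes are joined by and/or. There is no order of precedence and no need for a second source.

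Inclusion criterion 2 requires each woman to be "confirmed HIV-positive or on ART". Criterion 4 is "male partner is of HIV- or unknown status". Study Objectives gives intervention women counselling on kit use and "2 HIVSSs with HIVSS instructions and invitation to return for confirmatory testing". The Male partner contact paragraph speaks of a single kit. The number of kits must be reconciled.

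Outcome 3 is the percentage of partners with a positive screening or test result. It has no evidence list of its own. The follow-up row of Table 1 covers uptake, positivity and linkage, and names the telephone and health records as sources.

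**The concern.** A used kit shows that someone was tested, not who. The person holding the kits is known to be HIV-positive and has just been shown how to use them. She may use one innocently, to demonstrate it or to test alongside her partner. The male endline survey itself mentions linking self-screening to couples testing.

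If that kit is returned or photographed, outcome 2(i) as written can record a tested partner. Only intervention-arm women receive kits, so the error has no counterpart in the standard-of-care arm and can only favour the intervention. If the kit is reactive and is taken as the partner's result, outcome 3 is affected as well.

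The background section names validation of partner use and results as a research gap, and the pilot is meant to inform a larger trial. Evidence that looks objective but has no known user would carry forward into that trial.

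**Working it through.** The plan gives no expected rates, significance level, power or analysis test, so there is no figure of its own to reproduce. The check is mainly one of text. The sizes below are illustrations on assumed inputs.

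**1. Is any kit tied to its user?** The documents describe no kit label, observed use, partner confirmation or required confirmatory test. Four partial checks exist, and none is a condition for counting outcome 2:

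- The name and date-of-birth check (Male partner contact) identifies the man for telephone consent. It does not link him to a kit.
- Giving his telephone number is optional (Informed consent).
- The male survey seeks 20 men, 10 of them non-users.
- Confirmatory testing is invited and asked about at endline.

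**2. When does the kit route add error?** Take a partner who did not test and a kit that the woman used and supplied.

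| Her report | Outcome 2 under the current rule | Does the kit add error? |
|---|---|---|
| He tested | Met by her report alone | No; the error is false self-report, possible in both arms |
| He did not test | Can be met by the kit; no conflict rule | Yes |
| No report | Met by the kit or photo | Yes |

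The added error is confined to the last two rows.

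**3. Size for outcome 2.** Let k be the number of women in those two rows, out of 50 (Study design). The inflation is k/50 in the intervention arm and 0 in the other. Assume k = 1 to 5: 1/50 = 2 points, 5/50 = 10 points.

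**4. Size for outcome 3, if such kits are counted there.** Assume 8 of 50 partners are truly positive (16%), and that a kit used by an index woman is reactive with probability s. The apparent rate is (8 + k × s)/50.

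| s | k = 1 | k = 5 |
|---|---|---|
| 0.5 | 8.5/50 = 17.0% | 10.5/50 = 21.0% |
| 0.8 | 8.8/50 = 17.6% | 12/50 = 24.0% |
| 1.0 | 9/50 = 18.0% | 13/50 = 26.0% |

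With tested men as the denominator, assume 25 tested and 7.5 expected positives (30%). Five miscounted men give (7.5 + 5s)/30. That is 33% at s = 0.5, 38% at 0.8 and 41% at 0.95. On this denominator the rate rises only if s exceeds 0.30, since (7.5 + 1.5)/30 = 30%.

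**5. Size against the trial's precision.** Assume a two-sided 5% test of two proportions, which the plan does not specify. With 50 per arm, 80% power needs a difference of about 25 to 28 points for control rates of 20% to 60%. Now let true testing be p in both arms, with a share f of untested intervention partners miscounted. The intervention rate becomes p + f(1 − p), and the extra men number 50f(1 − p). Exact chance of a significant pooled z-test:

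| p | Extra men, f = 10% / 20% | f = 0 | f = 10% | f = 20% |
|---|---|---|---|---|
| 0.3 | 3.5 / 7.0 | 0.050 | 0.113 | 0.307 |
| 0.4 | 3.0 / 6.0 | 0.052 | 0.100 | 0.241 |
| 0.5 | 2.5 / 5.0 | 0.057 | 0.088 | 0.184 |
| 0.6 | 2.0 / 4.0 | 0.052 | 0.071 | 0.132 |

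A handful of miscounted kits is thus small next to the detectable difference, but enough to move the error rate above its nominal level.

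**The case against.** The strongest reply is that index self-report alone already meets outcome 2 in both arms. A woman who wanted to please staff would need no kit, and one who used a kit out of curiosity can say at endline that he did not test. This largely stands. It limits the kit problem to the last two rows of the table in step 2, where the plan has no rule.

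Other points also stand:

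- The background section cites a review in which returned kits and photographs may be able to verify results, and the pilot uses both. It also says that better verification is urgently needed.
- The questionnaires are not in the documents and may already ask who used the kit. Even so, the outcome rule makes no use of the answer.
- Error rates presume a hypothesis test, while the aim is preliminary efficacy.

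A reader might infer more than the text supports:

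- **That every index woman holds kits.** Only the 50 in the intervention arm do.
- **That a kit she used would probably read positive.** Her HIV status makes this plausible, but the documents give no kit sensitivity, including in women on ART.
- **That outcome 3 expressly accepts such a kit.** The evidence list sits under outcome 2, and Table 1 can be read as using health records for positivity too.

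**Conclusion.** The concern holds in a limited form. The stated rule can count a kit used by the index woman as a partner test, in the intervention arm only, when the kit is counted without, or against, her report that he tested. An effect on outcome 3 is possible, but depends on how that outcome is ascertained, which the plan leaves open.

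The size is unknown. The 2 to 10 points for outcome 2 rest on an assumed 1 to 5 women. The 17% to 26% for outcome 3 also rests on an assumed true rate of 16% and assumed reactivity. None of these figures estimates a bias that is known to be present. The defect is that the definition could not detect such a bias. It is worth correcting because the remedy is cheap and removes the non-deliberate misattribution.

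**What to change.** 1. Add one endline item per kit: used by the partner, the index woman, someone else, or unused.
2. Label each kit with participant ID and kit number, so that a photo or returned kit can be matched to that answer. Reconcile the number of kits given.
3. In outcome 2(i), count a kit or photo supplied by the index woman only when the partner is recorded as its user. Where sources conflict, the kit alone does not count.
4. For outcome 3, apply one standard in both arms. Report positives confirmed by a facility result or health record separately from unconfirmed positives, and exclude kits recorded as used by the index woman.

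Partner confirmation should not be demanded only for kits supplied by index women. A verbal report of a positive result in the standard-of-care arm would face no such test. Partner contact details are also optional, and calls about a positive result touch the confidentiality and violence risks that the protocol lists.

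The cost is one survey item, labels and a few sentences of outcome wording. Counted uptake and positivity may be slightly lower, because kits with no recorded user drop out. Reporting outcome 2 under both the current and the revised rule would show the difference. The item is still the woman's own report and a label identifies a kit rather than its user, so deliberate substitution and false self-report should be stated as limitations.

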- First, there is an urgent need to examine secondary distribution of HIVSS by women to male partners in **South Africa**. Few HIVSS studies have been conducted in South Africa which has very different epidemic and contextual factors (e.g., higher levels of IPV) versus Kenya and Malawi where most previous studies were conducted. In contrast to the higher acceptability of HIVSS reported by clients in Kenya and Malawi (17) some studies from South Africa indicate that acceptability may be low which could greatly limit HIVSS impact, while other studies indicate that acceptability may be high in South Africa (18). To our knowledge, no randomized controlled trials of the effectiveness of secondary HIVSS distribution have taken place among South Africa adults.
- Second, more research is needed to **validate partner HIVSS use and results** after distribution. A systematic review found that three strategies may be able to verify HIVSS results (supervision by a health provider, returning used kits, and electronic transmission of photographs), but evaluation and development of innovative strategies for verifying HIVSS use and results is urgently needed (19).

- Finally, prior trials of HIVSS have focused on primary outcomes of HIVSS uptake among partners. It is additionally and critically important to understand whether HIVSS strategies lead to **improved partner ART uptake** among newly diagnosed men.

COVID-19 and study implications. The Department of Health and PEPFAR partners, including BroadReach Healthcare, have continued to offer HIV testing, treatment and monitoring during the COVID-19 lockdown in South Africa as HIV services are essential health services. The team will continue to observe all Department of Health infection prevention and control methods. The proposed intervention is important during the COVID-19 lockdown as it is designed to promote HIV testing and case finding from home to improve linkage to treatment from the HIV+ partner.

3. Study Objectives:

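### The primary outcome lists a partner's arrival at the facility with a slip as a stand-alone source without requiring a test, so a man who attends untested can be counted as tested.

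*Combined protocol and SAP*

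**What the plan says.** The Evaluation section defines outcome 2 as the percentage "of male partners who either screened or tested for HIV assessed at 3 months after randomization (primary outcome"). Item (i) then gives the sources. It opens with "Outcome measured via: index or partner self-report, SMS/WhatsApp of a picture of the used HIVSS sent by partner or index". Next comes handing the used kit back at the clinic, by either member of the couple. The last source, added with an and/or, is "partner coming into facility for with an invitation for confirmatory testing or SOC counseling referral". Aim 2b(i) under Study Objectives gives the same list, with the same broken phrase.

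The two slips are issued differently. According to the Study Objectives, intervention women receive "2 HIVSSs with HIVSS instructions and invitation to return for confirmatory testing". According to the Standard of care arm paragraph, control women receive counselling and a "referral for her partner(s) to return to the facility for testing".

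Table 1 says that follow-up at about 3 months will evaluate testing uptake, results "positivity) and linkage (telephonically and using health records"). The background section, in its second listed gap, says that "evaluation and development of innovative strategies for verifying HIVSS use and results is urgently needed".

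**The concern.** The outcome is an act: the man screened himself or was tested. The kit-based sources are tied to that act, because the photo and the returned device must be of a used kit. The facility source carries no matching condition. It names arrival with a piece of paper, and neither a performed test nor a recorded result is required.

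A man may present and then decline, or leave before the test. Staff who apply the list as written could score him as a success. In the standard-of-care arm the trial supplies no kit, so the photo and kit-return sources do not apply to the planned pathway. That leaves self-report and arrival with the referral, and the referral is by design handed over before any test. In the intervention arm the invitation is given out together with the kits. Carrying it suggests a self-screen but does not prove one.

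At stake is the accuracy of the primary outcome in a small pilot meant to inform a larger trial, in a setting where the background itself names verification as a gap.

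**Working it through.** The plan gives no assumed testing rates, power or sample-size derivation, so there is no figure to reproduce. The check has two parts.

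**1. Sources by arm** (Evaluation, outcome 2(i), set against the arm descriptions)

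| Source | Intervention | Standard of care | Shows a completed screen or test? |
|---|---|---|---|
| Index or partner self-report | yes | yes | by statement only |
| Photo of used kit | yes | no kit supplied | yes, kit used |
| Return of used kit | yes | no kit supplied | yes, kit used |
| Arrival with invitation or referral | yes | yes | not required by the wording |

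In the standard-of-care arm, the only listed source other than self-report is arrival. The documents contain no ranking of sources, no adjudication rule and no instruction for a man who attends and is not tested.

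**2. Size**

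Inputs:
- 50 women per arm (Study design: "Randomized control trial of n=100 WLHIV (50 in each arm) in two facilities in the Nkangala district").
- One partner per woman (assumption; the plan sometimes writes partner(s)).
- m_INT and m_SOC: the numbers of men per arm counted on attendance alone who neither screened nor tested (unknown).

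Each such man adds 1/50 = 2 percentage points to his arm. Therefore:

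observed difference = true difference + 2 × (m_INT − m_SOC) points.

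Illustrations, with assumed true rates and assumed counts:

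| True SOC vs intervention | m_SOC | m_INT | Observed rates | Observed difference |
|---|---|---|---|---|
| 30% vs 60% (30 points) | 1 | 1 | 32% vs 62% | 30 |
| 30% vs 60% | 5 | 1 | 40% vs 62% | 30 + 2 × (1 − 5) = 22 |
| 30% vs 60% | 1 | 5 | 32% vs 70% | 30 + 2 × (5 − 1) = 38 |
| 50% vs 75% (25 points) | 5 | 1 | 60% vs 77% | 25 + 2 × (1 − 5) = 17 |
| 50% vs 75% | 1 | 5 | 52% vs 85% | 25 + 2 × (5 − 1) = 33 |

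A milder case: if 15 to 20 men in one arm attend with a slip and 10% of them leave untested (both assumed), that arm gains 0.10 × 15/50 = 3.0 to 0.10 × 20/50 = 4.0 points.

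For scale, at 30% vs 60% the 95% interval on the difference has half-width 1.96 × √(0.3 × 0.7/50 + 0.6 × 0.4/50) = 1.96 × 0.095 ≈ 0.19, or about 19 points.

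**The case against.** The strongest reply is that item (i) lists how the outcome is measured and does not redefine it. The parent definition still says screened or tested, and a man who attends and declines has done neither. The phrase is also visibly broken: a word is missing after *for*, and *testing* is a plausible candidate. Both slips are issued for testing, and Table 1 names health records as a means of follow-up.

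Much of this stands. A reader might infer that the plan has a rule under which untested attenders count as tested. It does not; it leaves the case open. But item (i) is the only operational text. Attending for testing is still not a completed test, and health records are not among the sources in 2(i). Table 1 shows that a record check is feasible, not that it governs the primary outcome.

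It is also fair to say that a few points are small against the sampling error of a pilot of this size. That limits the weight of the point. It does not remove it, because this error comes from the definition and would carry over to a larger trial built on it.

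The change leaves self-report as an unverified source. That is true, and it is a separate matter.

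**Conclusion.** The point holds as a gap in the outcome definition. Attendance with an invitation or referral is accepted as a stand-alone source without a documented test, so a literal reading can score an untested man as tested. The size is 2 percentage points per man in his arm, given 50 per arm and one partner per woman. How many such men there would be is unknown, and every count and rate in the illustrations is assumed.

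Two stronger readings are tempting and are not supported:
- **That the error shrinks the difference.** Referral attendance is the control arm's designed route, so a reader might expect false events to gather there. The slip is weak evidence in both arms, however, and the documents give no data on untested attenders. The difference could shrink, grow or stay the same.
- **That outcome 3 is contaminated.** That outcome is the percentage of male partners with a positive result. The plan states no denominator of tested men, so the claim would rest on one that the reader supplies.

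Nor does the Human Resources paragraph show that test status is known to study staff at the partner's visit: it describes counsellors who select, consent and interview the women.

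**What to change.** In Aim 2b(i) and outcome 2(i), repair the broken phrase and replace the attendance source with: *partner HIV test recorded in facility records at a visit made with the invitation or referral*.

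Add two rules, identical in wording for both arms:
- Attendance without a recorded test is logged separately and does not by itself count as the outcome.
- A kit-arm man who attends with his invitation and has no facility test still counts if another listed source (self-report, photo or returned used kit) shows his self-screen. Without this rule the change could discard true self-screens, and only in the intervention arm.

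The text change is a few sentences in two places, and health records are already a planned source in Table 1. The small downside is the work of matching slip visits to facility records in both arms. The Male partner contact section describes contact and consent steps for partners in the intervention arm, so the plan should also say how the match is made for standard-of-care partners.
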